## • Primary Efficacy Endpoint

Following the American Association for the Study of Liver Diseases-Journal of the National Cancer Institute guidelines for trial design in HCC, we have set our primary endpoint as TTR, according to the recommendation for Phase II studies that assess adjuvant therapies secondary to liver directed therapy (33). TTR will be defined as the time from randomization to the first occurrence of a documented HCC recurrence or HCC death, within the 12-month intervention and assessment period. Participants who experience death attributed to their underlying liver cirrhosis, or other cause, will be censored at death date. For participants who do not recur or die and are lost to follow-up prior to the 12-month study visit, analysis of TTR will be censored at their last date of evaluable scan before drop-out.

In this study, we will rely heavily on the mRECIST outcome guidelines and the Liver Imaging Reporting and Data System (LI-RADS) diagnostic algorithm for defining hepatic recurrence (34, 35), and central expert independent radiographic review by MedQIA.

Pathological Definition: Participants who receive a transplant will become ineligible at the time of transplantation. Recurrent HCCs may also be identified at time of transplantation during the examination of the explant by a pathologist. These "incidental" HCCs represent a sizable proportion, amounting to 22% of HCCs among those receiving a liver transplant. Thus, if transplantation occurs and a pathologically confirmed HCC is detected, we will examine these pathologically defined tumors as a **secondary** definition of recurrence.

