## 3.1.3 Central Imaging Review (MedQIA)

Imaging will be conducted throughout the duration of the study as standard clinical care for HCC surveillance (recurrence or metastasis) and will be no cost to the study. All standard of care imaging scans (MRIs, CTs, or ultrasounds) will be sent to the central imaging core laboratory (MedQIA) and reviewed per the *Imaging Charter*. Assessment of eligibility and HCC recurrence will be made by an independent team of reviewers outside of the patient's care team, coordinated by our imaging core laboratory (MedQIA), per the *Imaging Charter*. Image procedures, acquisition, and transfer guidelines will be harmonized across the clinical sites by MedQIA and the study team. MedQIA uses proprietary computer-aided technologies for image analysis to maximize accuracy and reproducibility and reduce adjudication rates. Tumor measurements will be computed from radiologist-approved volumetric contours, providing data on diameter, volume, density, and heterogeneity. MedQIA was chosen for this study given their past performance, including serving as the imaging core for oncology clinical trial submissions to the FDA with imaging as the primary endpoint.

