## 5.9 Duration of Follow Up

Clinical research staff will make follow-up telephone calls to study participants on days 30  $\pm$  7, 60  $\pm$  7, and 90  $\pm$  7 after completion of Study Visit 6 to assess symptoms and adverse events. For all patients who enter the trial and receive a liver transplant before the end of this 5-year study (within or beyond the 12-month intervention period), we will obtain specimens at the time of transplantation.

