## 6.4 Schedule of Events Table

+ Abdominal imaging results will be reviewed during pre-screen medical chart review to determine initial eligibility. At study visits 3-6, all standard of care images occurring since screening or the last study visit will be reviewed.

#Telephone contact once a month ( $\pm$  3 days) during the intervention to assess compliance and adverse events.

^Follow-up telephone contact on days  $30 \pm 7$ ,  $60 \pm 7$ , and  $90 \pm 7$  after completion of Study Visit 6 to assess adverse events.

% Unscheduled liver transplant may occur at any time post-intervention depending on the date of the transplant.

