## 9.3.1 Analysis of Primary Endpoint: TTR

The log-rank test will be carried out to compare the distributions of TTR between placebo and pravastatin groups and the Kaplan-Meier estimators will be presented graphically. Cox proportional hazards model will be fitted to the data where the explanatory variable of interest is the indicator of treatment allocation adjusting for clinical and demographic baseline covariates, including sex. Patients who did not experience HCC recurrence, or receive a liver transplant and are still alive at the end of the study will be right censored. Patients who are transplanted or die before HCC recurrence will be treated as a competing risk. A competing risk model for TTR will be used to estimate the cumulative incidence of TTR using time to transplant or death as a competing risk. The proportional hazards assumption will be tested graphically and analytically, and model diagnostics such as martingale and Schoenfeld residuals will be conducted to assess model adequacy. Violation of the proportional hazards assumption will be addressed by use of time-dependent covariates or extended Cox models. The possibility of collinearity among the explanatory variables will be reduced after careful assessment of the correlation matrix and condition index. Automatic variable selection methods in a multivariable Cox proportional hazards model such as stepwise, backward, and forward will be used as a guideline to identify sets of important predictors and a more rigorous approach based on a 4-step procedure outlined in Collett (2003) will be employed (55). Power. Preliminary data indicate that the 12-month RFS is between 57% and 78% in patients with: 1) Child Pugh A or B cirrhosis, 2) small HCCs (typically meeting Milan criteria) 3) liver directed therapy (typically RFA or resection), and 4) no other interventions (27, 56-59). Therefore, we will assume that the 12-month RFS in the control group is 65%. Assuming a common cumulative incidence of the competing risk events at 12 months of 20% (10% due to liver transplant and 10% due to death), a 42-month accrual time and 15-month follow up time, and 10% drop out, data from 47 patients per group achieve 80% power to detect a hazard ratio of 0.45 using a two-sided log-rank test with a 0.1 level of significance. This is equivalent to detecting a decrease in the 12-month cumulative incidence of disease recurrence from 35% in the control group to 18% in the treatment group, which is clinically meaningful. The choice of a type I error rate of 0.1 is appropriate for a randomized phase II trial since this can serve as a randomized screening design for a nondefinitive comparison of statin vs placebo (reference: Mandrekar and Sargent (2010)). We further assumed that TTR and time to death or transplant are independent and exponentially distributed. Statistical power was based on the formulas in Machin et al. (2008) and Pintilie (2006) and were carried out using PASS version 13 (60, 61).

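### The 80% power stated for time to recurrence relies on recurrences after month 12, which the endpoint definition excludes; on a 12-month endpoint power is about 70–74% with 65 per group, or 58–62% with 47

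*Combined protocol and SAP*

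**What the plan says.** Section 2.3 (Primary Efficacy Endpoint) runs time to recurrence (TTR) from randomization to the first "documented HCC recurrence or HCC death, within the 12-month intervention and assessment period". Section 3.0 sets active participation at 12 months. In Section 6.4 the last imaging review is at Visit 6 (month 12): "At study visits 3-6, all standard of care images occurring since screening or the last study visit will be reviewed". The calls at days 30, 60 and 90 are made "after completion of Study Visit 6 to assess symptoms and adverse events" (Section 5.9). Section 4.5 gives 3 years of recruitment, and Section 9.2 expects evaluable participants to have finished all procedures within 4 years, which fits 36 + 12 = 48 months.

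The power paragraph in Section 9.3.1 uses a different time frame: "a 42-month accrual time and 15-month follow up time, and 10% drop out, data from 47 patients per group achieve 80% power" at hazard ratio 0.45, two-sided 0.10. It equates this effect with "a decrease in the 12-month cumulative incidence of disease recurrence from 35% in the control group to 18% in the treatment group".

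Other places are looser. Section 9.3.1 says that patients without an event who are "still alive at the end of the study will be right censored". Section 3.1.3 says "Imaging will be conducted throughout the duration of the study as standard clinical care for HCC surveillance". Section 3.0 expects the study to last 5 years.

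Sections 3.0 and 9.2 describe 47 per group as what remains of 65 after drop-out and competing events.

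**The concern.** The power of a log-rank test depends on the number of events. An accrual period of 42 months plus 15 months of follow-up, read in the usual way, follows each patient for between 15 and 57 months and counts recurrences throughout. The endpoint definition stops at month 12, and nothing in the schedule collects recurrence data for TTR after that. If the definition governs, the calculation includes events that the primary analysis will not contain.

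At stake is how a negative trial is read. In a phase II screening trial a null result may end development, and it would be judged against a power that the test does not have. The choice also decides which recurrences count in the primary analysis, so it should be settled before any unblinded look at the data.

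**Working it through.** **Inputs (Section 9.3.1 unless noted).** Control 12-month recurrence 35%; competing events 20% in both groups; hazard ratio 0.45; two-sided 0.10; 10% drop-out; independent exponential times. 65 per group randomized, 47 analytic (Section 9.2).

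**Rates per year**, reading 35% and 20% as cumulative incidences. The total is −ln(1 − 0.35 − 0.20) = 0.799. Recurrence is 0.799 × 0.35/0.55 = 0.508; competing events 0.799 × 0.20/0.55 = 0.290; drop-out −ln(0.9) = 0.105. With 0.45 × 0.508 in the pravastatin group and no drop-out, the 12-month incidences are 0.350 and 0.178, which returns the plan's 35% and 18%.

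**Events needed for 80% power.** Schoenfeld: 4(1.645 + 0.842)²/(ln 0.45)² = 38.8. Freedman: (1.645 + 0.842)² × (1.45/0.55)² = 43.0.

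**Event probability per group** = (recurrence rate/L) × [1 − mean of exp(−L·t)], where L is the sum of that group's recurrence, competing and drop-out rates and t is follow-up in years. Expected events D = n × (sum over the two groups). Power is Φ(½√D·|ln 0.45| − 1.645) by Schoenfeld and Φ(√D × 0.55/1.45 − 1.645) by Freedman.

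**Reproducing the stated figure, then applying the 12-month limit**

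| Follow-up | n per group | Events | Schoenfeld | Freedman |
|---|---|---|---|---|
| 42-month accrual + 15 | 47 | 37.8 | 79.1% | 75.4% |
| Fixed 15 months | 47 | 27.2 | 66.9% | 63.1% |
| Fixed 15 months | 65 | 37.6 | 78.9% | 75.2% |
| 12 months | 65 | 32.8 | 73.9% | 70.1% |
| 12 months | 47 | 23.7 | 61.8% | 58.0% |

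With the stated 47, only the long follow-up comes close to 80%. A fixed 15 months (12 months plus the 90-day calls) does so only with 65, and it too counts recurrences after month 12. At 12 months the event probabilities with drop-out are 0.3345 and 0.1701, so D = 65 × 0.5046 = 32.8. Log-rank simulation on this basis (10,000 runs) gives 72.5% with 65 and 59.3% with 47 at 12 months, and 77.6% for 42 + 15 with 47.

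**A check without a drop-out model.** The plan's own incidences sum to 0.35 + 0.18 = 0.53. That gives at most 65 × 0.53 = 34 events, or 47 × 0.53 = 25, before any loss, against the 39 to 43 needed.

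**Which n.** 65 × 0.9 × 0.8 = 46.8, so the 47 already removes drop-out and competing events. The power model then applies both again. For that reason 65 is taken as the main basis here.

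**Sensitivity at 12 months.** Across other readings of the rates (for example, 35% and 20% as marginal risks) and of drop-out, power is 64–76% with 65 per group and 52–64% with 47. Over the plan's own range for control 12-month recurrence-free survival, with 65 per group, power is 82–78% at 57% (40.9 events) and 56–52% at 78% (20.2 events). With 65 per group, 80% power is reached at a hazard ratio of 0.415 (Schoenfeld) or 0.385 (Freedman). At hazard ratio 0.45, 80% would need 77 or 86 per group.

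**The case against.** **Section 2.3 need not govern.** The analysis section censors at the end of the study, imaging continues throughout, and the long follow-up is an inference about software output that cannot be seen. This stands as a reason to call it a conflict and to state the shortfall conditionally. It does not remove the conflict, because the endpoint definition still excludes the later events.

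**A limit of exactly 12 months is too strict.** Randomization is at Screening (Section 6.1.1), Visit 1 comes up to 30 days later, and Visit 6 has a 15-day window, so assessment can end near 13.5 months. With 65 per group and 10% loss that gives 76.7% to 72.9%. Missed visits can be rescheduled for up to 2 months (Section 4.5), so the extreme is about 15 months, which gives 78.9% to 75.2%. Few patients would reach that extreme, and with 47 it still gives only 67% to 63%.

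**HCC deaths are events in Section 2.3, while Section 9.3.1 treats all deaths before recurrence as competing.** The documents give no split. Assuming that 2, 5 or all 10 points of the 10% death incidence become events, power with 65 per group is 76–72%, 79–75% or 83–80%. Only the last, extreme case reaches 80%; with 47 the maximum is 72%.

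**The errors offset each other.** This is true in part. With 65 per group, the 42 + 15 design would give 89–86%, so the double discount made the plan look worse. Once events stop at month 12, the follow-up assumption outweighs it.

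**This is a non-definitive phase II trial, and uncertainty in the control rate moves power more.** Both statements are true. Neither makes the stated figure correct for the stated endpoint.

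**Conclusion.** The concern holds. The 12-month endpoint and the 80% power statement cannot both stand. If Section 2.3 governs, power at hazard ratio 0.45 is about 70–74% with 65 per group (about 33 events), or 58–62% with the stated 47 (about 24 events). This rests on 35% and 20% as 12-month cumulative incidences, exponential times and 10% exponential drop-out. Visit windows and a moderate share of HCC deaths narrow the gap without closing it. Among the plan's own control rates, 80% is reached only near the most favourable end. Type I error and bias are not affected. It must be fixed because the figure is wrong for the primary endpoint as defined.

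**What to change.** Choose one follow-up rule and make the sections agree.

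**Option A, preferred because it needs no assumption about the effect after study drug stops.** Keep the 12-month TTR. In Section 9.3.1, replace the 42- and 15-month assumptions with a statement that:

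- TTR is censored at 12 months;
- with 65 per group, 12-month incidences of 35% (control recurrence) and 20% (competing events) and 10% exponential drop-out, about 33 recurrences are expected at hazard ratio 0.45;
- the two-sided 0.10 log-rank test then has about 70–74% power, and 80% power at a hazard ratio of about 0.38 to 0.42.

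If 47 stays as the base, state about 24 recurrences and 58–62%. Add one line of sensitivity for visit windows and HCC deaths. The cost is rewording and a less favourable stated power.

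**Option B.** Count recurrences to the end of the study. Write this into Section 2.3 and the Section 6.4 schedule, with central review of standard-of-care scans after Visit 6. With 65 per group, 36-month accrual and closure 12 months after the last entry, about 49–50 events and 85–88% power are expected, provided hazard ratio 0.45 persists after treatment ends at month 12. About 17 of those events fall after month 12. In simulation, power is 87% if the effect persists, 72% if the later hazard ratio is 0.7, and 52% if it is 1.0; these last two values are illustrative assumptions. The cost is the extra central reads and possible dilution of the effect.

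Under either option, no patients are added. Also align the Study Summary's restriction of the primary analysis to 12-month completers, the meaning of 47 in Sections 3.0 and 9.2, the handling of HCC death in Sections 2.3 and 9.3.1, and the censoring rule and 42-month accrual in Section 9.3.1 (against 3 years in Sections 4.5 and 9.2).

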# 9.3.2 Analysis of Secondary Endpoints RFS and OS

For the secondary objective, comparison of overall survival and recurrence free survival between the pravastatin and placebo groups will be achieved by fitting a Cox proportional hazards model as described above for TTR. In this analysis, a competing risk model will

be fitted to the data using time to transplant only as a competing risk since overall survival includes death from any cause.

**Waitlist drop-off.** Fischer's exact test will be used to compare the proportions of patients on the waitlist who drop off between the pravastatin and placebo group. We expect about 35% of patients in the placebo group to drop off due to various causes such as death and HCC progression beyond Milan. Data from 47 patients per group achieve 80% power to detect a decrease in drop-off rates from 35% in the control group to 14% in the treatment group using a one-sided Fisher's exact test at the 0.1 level of significance.

Liver stiffness and Liver fat fraction. The two-sample t-test will be used to compare the change in liver stiffness/fat fraction from 3 to 12 months between pravastatin and placebo groups. If the distribution of the change in liver stiffness/fat fraction is highly skewed so that the sample mean based on 47 measurements is not approximately normally distributed, the Mann-Whitney test will be used instead. Measurements of liver stiffness vary between 1.5 and 75 kPa. Therefore, we conservatively estimate the standard deviation of liver stiffness at 3 months as (75-1.5)/4 = 18.4. If X and Y denote the random variables of liver stiffness at 3 and 12 months, respectively, the Var(Y-X) = Var(X)+Var(Y)-2p Var(X) Var(Y), where p is the correlation coefficient between X and Y. Assuming a non-negative correlation between the measurements at 3 and 12 months and the same variance at 12 months  $\sigma$ 2, then a conservative estimate for the standard deviation of the change in liver stiffness is 1.4  $\sigma$ . Therefore, data from 47 patients per group achieve 80% power to detect an effect size of 0.5 using a two-sided two-sample t-test with 0.1 level of significance. We therefore have enough patients to detect clinically meaningful differences in mean liver stiffness. Here, the effect size is the ratio of the difference in the mean change between the two groups relative to the baseline standard deviation  $\sigma$ assumed to be the same for the treatment and control groups. Linear regression analysis will be carried out to estimate the adjusted pravastatin effect if there is evidence of imbalance between the two groups with respect to one or more baseline clinical and demographic covariates.

**Change in biomarkers.** Two-sample t-test will be carried out to compare the change in biomarkers from baseline to each of the two follow-up time points, 6 and 12 months, between treatment and placebo groups. The Man-Whitney test will be used in the presence of highly skewed distributions and Fisher exact test will be used for dichotomous stratifications (high versus low). Assuming a common standard deviation of the change in biomarker from baseline to each time point between the two groups SD(diff), data from 47 patients per group achieve 80% power to detect an effect size of 0.72 using a two-sided two-sample t-test with a Bonferroni corrected 0.01 level of significance since we plan to test 10 biomarkers (0.1 / 10). Here, the effect size is the ratio between the difference in change of biomarkers between the two groups over SD(diff). Linear or logistic regression analysis will be carried out if there is evidence of imbalance between the two groups with respect to one or more baseline clinical and demographic covariates at each time point as in Aim 3.

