## 1.3 Rationale

Cirrhosis affects nearly 633,000 Americans, and HCC is a leading cause of death in nonsymptomatic patients with cirrhosis (5, 31, 32). Less than 5% of patients with cirrhosis and HCC are candidates for liver resection due to the high degree of underlying liver dysfunction, which makes liver transplantation (LT) the definitive and curative treatment of choice. In 2015, 15,000 person-years were spent awaiting LT in the U.S. and only 6,600 patients received LT, underscoring the major competition among patients with cirrhosis for LT. Although patients with HCC receive priority listing for LT if they meet Milan/United Network for Organ Sharing (UNOS)  $T_2$  criteria, the wait time often exceeds 1 year. Exacerbating the problem for patients with HCC, very recent changes to the national liver allocation policy (October, 2015) delay the assignment of Model for End Stage Liver Disease (MELD) exception points for 6 months after listing, and reduce the maximum value of exception points to 34 for those with HCC. MELD is a clinical score that is a validated predictor of survival among patients with advanced liver disease used to prioritize patients for LT, and exception points increase a patients MELD score and therefore chances for LT. These changes were intended to create a better balance in transplant opportunities between those with and without HCC, and allow observation of tumor behavior to avoid transplanting aggressive tumors too guickly. However, for patients with HCC, these policy changes translate to longer wait times and growing concern that the tumor biology may shift from less to more aggressive over time. "Bridging" locoregional therapies (LRTs) are utilized while a patient is on the waitlist for LT, however drop-out from the waitlist remains a problem largely due to tumor progression or recurrence to beyond accepted radiological criteria. For example, the cumulative recurrence rate 2–3 years after radiofrequency ablation (RFA), the most common LRT in patients with cirrhosis eligible for transplant, has been reported at 72%-80%. Novel therapeutics offered in conjunction with LRT that could achieve lower rates or delay time to recurrence, could maintain transplant candidacy for sufficient time to achieve treatment with LT.

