#### • Secondary Efficacy Endpoints

Secondary endpoints include recurrence-free survival (RFS), overall survival (OS), waitlist survival, liver stiffness, liver fat fraction, circulating biomarkers, and liver tissue biomarkers. Differences in secondary endpoints will be compared in the pravastatin and placebo groups.

1) RFS: We will assess the effect of pravastatin on RFS. RFS will be defined as the time from randomization to the first occurrence of a documented HCC recurrence, within the 12-month intervention and assessment period.

2) OS: We will examine the effect of pravastatin on OS (defined as the time from randomization to death from any cause).

3) Waitlist drop-off: We will evaluate the effect of pravastatin on reducing waitlist dropout due to any of the following causes: 1) HCC progression outside of Milan/T2 criteria, 2) cirrhosis progression (too sick to transplant), or 3) death.

Participants who are delisted for other reasons (such as positive alcohol test) will be censored at date of delisting.

4) Change in liver stiffness: We will evaluate the effect of pravastatin on withinperson change in liver stiffness, as measured by magnetic resonance elastography (MRE) or FibroScan, between Study Visit 1 (0 month) and Visit 6 (12 month). Within-patient consistency is required between Study Visits 1 and 6 with regards to liver stiffness testing modality (MRE or FibroScan).

5) Change in liver fat fraction: We will evaluate the effect of pravastatin on withinperson change in liver fat fraction, as measured by MRI-proton density fat fraction (PDFF), between Study Visit 1 (0 month) and Visit 6 (12 month).

6) Change in serum biomarkers of monocyte/macrophage and stellate cell activation: We will examine the effect of pravastatin on change in serum biomarkers including cytokines, chemokines, soluble receptors, and proteins (specifically, IL6, TNF $\alpha$ , sTNFRII, IL18BP, sCD163, IL10, IL17, IL-8, CCL17, TGF $\beta$ ).

7) Levels of liver tissue markers related to HCC: We will examine the effect of pravastatin on levels of liver tissue markers related to HCC including those in the Wnt/ $\beta$ -catenin pathway (specifically,  $\beta$ -catenin and glutamine synthetase).

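### Overall survival is defined as death from any cause, but its competing-risk analysis treats transplant as a competing event and so estimates death before transplant

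*Combined protocol and SAP*

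**What the plan says.** **Definition.** Under Secondary Efficacy Endpoints, section 2.3 describes the endpoint as "OS (defined as the time from randomization to death from any cause"). It makes no exception for deaths after transplant and sets no time limit. Section 2.2 places all secondary objectives at 12 months from baseline.

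**Analysis.** Section 9.3.2 compares OS between arms by "fitting a Cox proportional hazards model as described above for TTR". It then adds a competing-risk model, which will "be fitted to the data using time to transplant only as a competing risk since overall survival includes death from any cause". It does not say whether that model is cause-specific or subdistribution. The TTR section it refers back to (9.3.1) describes its own competing-risk model in these words: "A competing risk model for TTR will be used to estimate the cumulative incidence of TTR using time to transplant or death as a competing" (transplant and death being the competing events there).

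**Status after transplant.** For the primary endpoint, section 2.3 states: "Participants who receive a transplant will become ineligible at the time of transplantation". Section 6.6 lists transplant as a reason for stopping study agent and says that follow-up for safety and endpoint data continues where possible.

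**Role of transplant in the rationale.** Section 1.3 argues that a therapy which delays recurrence "could maintain transplant candidacy for sufficient time to achieve treatment with LT".

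**The concern.** A competing event is one after which the endpoint can no longer occur. Transplant can reasonably play that role for TTR, because section 2.3 makes a transplanted participant ineligible from that point. It cannot play that role for death from any cause, because a transplanted participant can still die. The reason given in 9.3.2, that OS already counts every death, explains why death is not a competing event. It gives no ground for making transplant one.

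Two things are at stake. First, the reported quantity would not be the endpoint in 2.3, and no section gives another analysis that explicitly counts deaths after transplant. Since the trial's rationale runs through reaching transplant, survival after transplant is a part of OS that readers will want to see. Second, in a cumulative-incidence or subdistribution model, the arm with more transplants shows fewer deaths before transplant even when the death rate is the same. A difference in transplant rate can then appear in the OS comparison.

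**Working it through.** The documents give no OS rate, hazard ratio, event count or power, so there is no stated OS figure to reproduce. The calculation below sizes the problem.

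**Inputs from the documents**
- 65 participants per arm (9.2).
- "competing risk events at 12 months of 20% (10% due to liver transplant and 10% due to death"), common to both arms (9.3.1). There the figures are competing events for recurrence. Using the 10% as the 12-month incidence of death before transplant is my approximation.

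**Assumptions**
- Constant hazards.
- No effect of pravastatin on death.
- A range of transplant hazard ratios between arms.
- A range of post-transplant mortality.

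**Step 1: hazards.** The total hazard is -ln(1 - 0.20) = 0.2231 per year. Split equally, d = t = 0.1116 per year for death and for transplant.

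**Step 2: deaths missed by 12 months.** Death before transplant is d/(d+t) × (1 - exp(-(d+t))) = 0.5 × 0.20 = 10.0%, or 6.5 of 65. If mortality is the same before and after transplant, death from any cause is 1 - exp(-0.1116) = 10.6%, or 6.9 of 65. The difference is about 0.4 deaths per arm. If post-transplant mortality is 0.5 to 2 times the pre-transplant rate, death from any cause is 10.3% to 11.1% (6.7 to 7.2 of 65), so 3% to 10% of all deaths are missed.

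**Step 3: shift from a transplant-rate difference alone.** Multiply the transplant hazard in one arm by k and leave d unchanged. Death before transplant by T years is F(T) = d/(d+kt) × (1 - exp(-(d+kt)T)). The apparent ratio is ln(1 - F for the arm with k) / ln(1 - F for the other arm).

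| k | F, 12 months | Ratio, 12 months | Ratio, 24 months | Ratio, 36 months |
|---|---|---|---|---|
| 1 | 10.0% | 1.00 | 1.00 | 1.00 |
| 1.32 | 9.8% | 0.98 | – | – |
| 1.5 | 9.7% | 0.97 | 0.95 | 0.92 |
| 2 | 9.5% | 0.95 | 0.90 | 0.85 |
| 3 | 9.0% | 0.90 | 0.81 | 0.73 |

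The value 1.32 is (100 - 14)/(100 - 35) = 86/65. It is the ratio of patients remaining listed under the waitlist drop-off rates in 9.3.2, and it assumes that transplants are proportional to those still listed. For k = 1.32, F = 0.1116/0.2588 × (1 - exp(-0.2588)) = 9.8%, and the ratio is 0.98.

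**Step 4: the same scenario in other analyses.** The cause-specific hazard ratio is d/d = 1.00 for every k, provided transplant is independent of death risk. The all-cause hazard ratio is also 1.00 when transplant does not change mortality.

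**Step 5: false rejection.** This used 4,000 simulated trials per setting, 65 per arm, no effect on death, and a two-sided log-rank-type test at 0.1 (the level the plan sets for the primary endpoint; it sets none for OS).

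| Horizon | k | Subdistribution | Cause-specific | All-cause |
|---|---|---|---|---|
| 12 months | 2 | 11.1% | 11.0% | 10.8% |
| 12 months | 3 | 10.9% | 10.0% | 10.4% |
| 36 months | 2 | 13.2% | 10.2% | 10.2% |
| 36 months | 3 | 20.9% | 9.8% | 10.0% |

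Simulation error is about 0.5 percentage points, so at 12 months the inflation cannot be told from none.

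**The case against.** The strongest reply is that nothing of practical size happens inside the trial's own window. Section 2.2 sets the secondary objectives at 12 months. The visits end there, with telephone calls to 90 days afterwards (5.9, 6.3). On that horizon even a doubled transplant hazard moves death before transplant only from 10.0% to 9.5%, about 0.3 of a death in 65. The plan assumes the same competing-event incidence in both arms. Section 1.3 says the wait often exceeds a year, and section 4.4 admits patients who are inactive on the list or ineligible for transplant. Both limit how far treatment could change transplant within 12 months. This objection stands as to size. It does not remove the mismatch between definition and analysis.

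Three stronger readings are tempting, and the documents do not support them.

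- A reader might infer that no planned OS analysis counts deaths after transplant. That follows for the competing-risk model. For the Cox model, 9.3.2 does not say whether follow-up stops at transplant, so the handling there is unstated.
- A reader might infer that a difference in transplant rate will produce a false survival effect. That needs a cumulative-incidence or subdistribution model. The link back to 9.3.1 suggests one, but 9.3.2 does not name it. The cause-specific hazard ratio stays at 1.00 if transplant is independent of death risk. That condition may itself fail, since section 1.3 describes MELD both as a predictor of survival and as the basis of transplant priority.
- A reader might take the 24- and 36-month ratios as the expected distortion. No visit schedules survival assessment that late. The OS definition has no cap, and the lost-to-follow-up rule in 6.7 mentions documenting survival over 2 years, but both the horizons and the doubled or tripled hazards are assumptions.

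**Conclusion.** The point holds as a conflict between the endpoint in 2.3 and the competing-risk analysis in 9.3.2. As written, that model answers a question about death before transplant and reports it as OS. The handling of transplant in the OS Cox model is left open.

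Within 12 months the numerical consequence is small: about 0.4 deaths missed per arm (0.2 to 0.7 over the range of post-transplant mortality tried), and an apparent ratio of 0.98 to 0.95 for a transplant hazard ratio of 1.32 to 2. It would grow only if OS follow-up runs past 12 months, which the definition permits but no visit schedules. The sizes rest on constant hazards, the plan's 10% and 10%, and the assumed transplant and post-transplant ratios. OS is a secondary endpoint without a power statement, and the primary result is not affected.

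**What to change.** **In 9.3.2**, analyse OS as time from randomization to death from any cause, regardless of transplant, with Kaplan-Meier curves, the log-rank test and a Cox model. Censor only at the date last known alive or at the end of a stated OS window. If death before transplant is of interest, report it under that name as a supportive endpoint, and say whether the model is cause-specific or subdistribution.

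**In 2.3**, state the OS window, since 2.2 says 12 months and the definition gives none. Add that transplant ends TTR assessment but not survival follow-up, which agrees with 6.6 and removes the doubt left by the ineligibility sentence.

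**Cost.** The analysis change is wording, with no effect on sample size or the primary analysis. The real cost is that vital status must be recorded for transplanted participants, about 13 of 130 by 12 months at the plan's rate (10% × 130). Section 6.6 already intends such follow-up, but only where possible, and the schedule lists only specimens and a telephone contact at transplant. The documents do not say that vital status after transplant is already held in site records, so its collection should be written in.
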